#### **7.1.2. ECG Changes**

A participant who meets either bulleted criterion based on the average of triplicate ECG readings will be withdrawn from the study intervention.

- QTcF >500 ms.
- Change from baseline: QTcF >60 ms and QTcF >450 ms.

If a clinically significant finding is identified (including, but not limited to, changes from baseline in QTcF after enrollment), the investigator or qualified designee will determine if the participant can continue in the study and if any change in participant management is needed. This review of the ECG printed at the time of collection must be documented. Any new clinically relevant finding should be reported as an AE.

#### **7.1.3. COVID-19**

If a participant has COVID-19 during the study, this should be reported as an AE or SAE (as appropriate) and appropriate medical intervention provided. Study treatment should continue unless the investigator/treating physician is concerned about the safety of the participant, in which case temporary or permanent discontinuation may be required.

It is recommended that the investigator discuss temporary or permanent discontinuation of study intervention with the study medical monitor.

### **7.2. Participant Discontinuation/Withdrawal From the Study**

A participant may withdraw from the study at any time at their own request. Reasons for discontinuation from the study include the following:

- Refused further study procedures,
- Lost to follow-up,
- Death,

- Study terminated by the sponsor,
- Investigator's decision,
- Pregnancy.

At the time of discontinuing from the study, if possible, an early discontinuation visit should be conducted. See the [SoA](#) for assessments to be collected at the time of study discontinuation and follow-up and for any further evaluations that need to be completed.

The early discontinuation visit applies only to participants who are enrolled/randomized and then are prematurely withdrawn from the study. Participants should be questioned regarding their reason for withdrawal.

The participant will be permanently discontinued from the study intervention and the study at that time.

If a participant withdraws from the study, they may request destruction of any remaining samples taken and not tested, and the investigator must document any such requests in the site study records and notify the sponsor accordingly.

If the participant withdraws from the study and also withdraws consent (see Section 7.2.1) for disclosure of future information, no further evaluations will be performed and no additional data will be collected. The sponsor may retain and continue to use any data collected before such withdrawal of consent.

### **7.2.1. Withdrawal of Consent**

Participants who request to discontinue receipt of study intervention will remain in the study and must continue to be followed for protocol-specified follow-up procedures. The only exception to this is when a participant specifically withdraws consent for any further contact with them or persons previously authorized by the participant to provide this information. Participants should notify the investigator in writing of the decision to withdraw consent from future follow-up, whenever possible. The withdrawal of consent should be explained in detail in the medical records by the investigator, as to whether the withdrawal is only from further receipt of study intervention or also from study procedures and/or posttreatment study follow-up, and entered on the appropriate CRF page. In the event that vital status (whether the participant is alive or dead) is being measured, publicly available information should be used to determine vital status only as appropriately directed in accordance with local law.

### **7.3. Lost to Follow-Up**

A participant will be considered lost to follow-up if the participant repeatedly fails to return for scheduled visits and is unable to be contacted by the study site.

The following actions must be taken if a participant fails to attend a required study visit:

- The site must attempt to contact the participant and reschedule the missed visit as soon as possible. Counsel the participant on the importance of maintaining the assigned visit schedule and ascertain whether the participant wishes to and/or should continue in the study;
- Before a participant is deemed lost to follow-up, the investigator or designee must make every effort to regain contact with the participant (where possible, 3 telephone calls and, if necessary, a certified letter to the participant's last known mailing address or local equivalent methods). These contact attempts should be documented in the participant's medical record;
- Should the participant continue to be unreachable, the participant will be considered to have withdrawn from the study.

## **8. STUDY ASSESSMENTS AND PROCEDURES**

### **8.1. Administrative and Baseline Procedures**

The investigator (or an appropriate delegate at the investigator site) must obtain a signed and dated ICD before performing any study-specific procedures.

Study procedures and their timing are summarized in the [SoA](#). Protocol waivers or exemptions are not allowed.

Safety issues should be discussed with the sponsor immediately upon occurrence or awareness to determine whether the participant should continue or discontinue study intervention.

Adherence to the study design requirements, including those specified in the [SoA](#), is essential and required for study conduct.

All screening evaluations must be completed and reviewed to confirm that potential participants meet all eligibility criteria. The investigator will maintain a screening log to record details of all participants screened and to confirm eligibility or record reasons for screening failure, as applicable.

Participants will be screened within 28 days prior to administration of the study intervention to confirm that they meet the study population criteria for the study. If the time between screening and dosing exceeds 28 days as a result of unexpected delays (eg, delayed drug shipment), then participants do not require rescreening if the laboratory results obtained prior to first dose administration meet eligibility criteria.

Every effort should be made to ensure that protocol-required tests and procedures are completed as described. However, it is anticipated that from time to time there may be circumstances outside the control of the investigator that make it unfeasible to perform the test. In these cases, the investigator must take all steps necessary to ensure the safety and

well-being of the participant. When a protocol-required test cannot be performed, the investigator will document the reason for the missed test and any corrective and preventive actions that they have taken to ensure that required processes are adhered to as soon as possible. The study team must be informed of these incidents in a timely manner.

If an IV catheter is utilized for blood sample collections, ECGs and vital sign assessments (PR, BP, and RR) should be collected prior to the insertion of the catheter.

For samples being collected and shipped, detailed collection, processing, storage, and shipment instructions and contact information will be provided to the investigator site prior to initiation of the study.

The total blood sampling volume for individual participants in this study is approximately 255 mL. The actual collection times of blood sampling may change. Additional blood samples may be taken for safety assessments at times specified by Pfizer, provided the total volume taken during the study does not exceed 550 mL during any period of 56 consecutive days.

To prepare for study participation, participants will be instructed on the information in the [Prior and Concomitant Therapy](#) sections of the protocol.

## **8.2. Efficacy Assessments**

Efficacy parameters are not evaluated in this study.

## **8.3. Safety Assessments**

Planned time points for all safety assessments are provided in the [SoA](#). Unscheduled safety measurements may be obtained at any time during the study to assess any perceived safety issues.

### **8.3.1. Physical Examinations**

A complete physical examination will include, at a minimum, head, ears, eyes, nose, mouth, skin, heart and lung examinations, lymph nodes, and gastrointestinal, musculoskeletal, and neurological systems.

A brief physical examination will include, at a minimum, assessments of general appearance, the respiratory and CV systems, and participant-reported symptoms.

Physical examinations may be conducted by a physician, trained physician's assistant, or nurse practitioner as acceptable according to local regulation.

Height and weight will also be measured and recorded as per the [SoA](#). For measuring weight, a scale with appropriate range and resolution is used and must be placed on a stable, flat surface. Participants must remove shoes, bulky layers of clothing, and jackets so that only light clothing remains. They must also remove the contents of their pockets and remain still during measurement of weight.

Physical examination findings collected during the study will be considered source record and will not be required to be reported, unless otherwise noted. Any untoward physical examination findings that are identified during the active collection period and meet the definition of an AE or SAE ([Appendix 3](#)) must be reported according to the processes in [Sections 8.4.1 to 8.4.3](#).

### **8.3.2. Vital Signs**

#### **8.3.2.1. Blood Pressure and Pulse Rate**

Supine BP will be measured with the participant's arm supported at the level of the heart, and recorded to the nearest mm Hg after approximately 5 minutes of rest. The same arm (preferably the dominant arm) will be used throughout the study. Participants should be instructed not to speak during measurements.

The same properly sized and calibrated BP cuff will be used to measure BP each time. The use of an automated device for measuring BP and PR is acceptable; however, when done manually, PR will be measured in the brachial/radial artery for at least 30 seconds. When the timing of these measurements coincides with a blood collection, BP and PR should be obtained prior to the nominal time of the blood collection.

Additional collection times, or changes to collection times, of BP and PR will be permitted, as necessary, to ensure appropriate collection of safety data.

Any untoward vital sign findings that are identified during the active collection period and meet the definition of an AE or SAE ([Appendix 3](#)) must be reported according to the processes in [Sections 8.4.1 to 8.4.3](#).

#### **8.3.2.2. Respiratory Rate**

Respiratory rate will be measured after approximately 5 minutes of rest in a supine position by observing and counting the respirations of the participant for 30 seconds and multiplying by 2. When BP is to be taken at the same time, respiration measurement will be done during the 5 minutes of rest and before BP measurement.

#### **8.3.3. Electrocardiograms**

Standard 12-lead ECGs will be collected at times specified in the [SoA](#) section of this protocol using an ECG system that automatically calculates the HR and measures PR interval, QT interval, QTcF, and QRS interval. All scheduled ECGs should be performed after the participant has rested quietly for at least 5 minutes in a supine position.

To ensure safety of the participants, a qualified individual at the investigator site will make comparisons to baseline measurements. Additional ECG monitoring will occur if a) a post dose QTcF interval is increased by  $\geq 60$  msec from the baseline **and** is  $> 450$  msec; or b) an absolute QT value is  $\geq 500$  msec for any scheduled ECG. If either of these conditions occurs, then 2 additional ECGs will be collected approximately 2 to 4 minutes apart to confirm the original measurement. If the QTc values from these repeated ECGs remain above the

threshold value, then a single ECG must be repeated at least hourly until QTc values from 2 successive ECGs fall below the threshold value that triggered the repeat measurement.

If a) a post dose QTcF interval remains  $\geq 60$  msec from the baseline and is  $> 450$  msec; or b) an absolute QT value is  $\geq 500$  msec for any scheduled ECG for greater than 4 hours (or sooner, at the discretion of the investigator); or c) QTcF intervals get progressively longer, the participant should undergo continuous ECG monitoring. A cardiologist should be consulted if QTcF intervals do not return to less than the criteria listed above after 8 hours of monitoring (or sooner, at the discretion of the investigator).

In some cases, it may be appropriate to repeat abnormal ECGs to rule out improper lead placement as contributing to the ECG abnormality. It is important that leads be placed in the same positions each time in order to achieve precise ECG recordings. If a machine-read QTc value is prolonged, as defined above, repeat measurements may not be necessary if a qualified medical provider's interpretation determines that the QTcF values are in the acceptable range.

ECG values of potential clinical concern are listed in [Appendix 8](#).

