**Diagnostic Assessments:**

8. A positive urine drug test. A single repeat for positive drug screen may be allowed.
9. Pregnant or breastfeeding women or evidence of positive pregnancy test at screening or Study Day -1.
10. History of HIV infection, hepatitis B, or hepatitis C; positive testing for HIV, HBsAg, or HCVA. Hepatitis B vaccination is allowed.
11. Participants with ANY of the following abnormalities in clinical laboratory tests at Screening as assessed by the study-specific laboratory and confirmed by a single repeat, if deemed necessary:
  - AST or ALT level  $\geq 1.5 \times$  ULN;
  - T bili  $\geq 1.5 \times$  ULN; participants with a history of Gilbert's syndrome may have a direct bilirubin measured and would be eligible for this study provided the direct bilirubin is  $\leq$ ULN.
12. Renal impairment as defined by an eGFR in adults of  $< 75$  mL/min. Based upon participant age at screening, eGFR or eCrCl is calculated using the recommended formulas in Section 10.7.2 to determine eligibility and to provide a baseline to quantify any subsequent kidney safety events.
13. Screening supine BP  $\geq 140$  mm Hg (systolic) or  $\geq 90$  mm Hg (diastolic) for participants  $< 60$  years; and  $\geq 150/90$  mm Hg for participants  $\geq 60$  years old, following at least 5 minutes of supine rest. If systolic BP is  $\geq 140$  or 150 mm Hg (based on age)

or diastolic  $\geq 90$  mm Hg, the BP should be repeated 2 more times and the average of the 3 BP values should be used to determine the participant's eligibility.

14. Screening supine standard 12-lead ECG that demonstrates clinically relevant abnormalities that may affect participant safety or interpretation of study results (eg, QTcF  $>450$  ms or QRS interval  $>120$  ms, complete LBBB, signs of an acute or indeterminate- age myocardial infarction, ST-T interval changes suggestive of myocardial ischemia, second- or third-degree AV block, or serious bradyarrhythmias or tachyarrhythmias). If the uncorrected QT interval is  $>450$  ms, this interval should be rate-corrected using the Fridericia method only and the resulting QTcF should be used for decision making and reporting. If QTcF exceeds 450 ms, or QRS exceeds 120 ms, the ECG should be repeated twice and the average of the 3 QTcF or QRS values used to determine the participant's eligibility. Computer-interpreted ECGs should be overread by a physician experienced in reading ECGs before excluding a participant.

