## 10.8. Appendix 8: ECG Findings of Potential Clinical Concern

ECG Findings That May Qualify as AEs

Marked sinus bradycardia (rate <40 bpm) lasting minutes.

New PR interval prolongation >280 ms.

New prolongation of QTcF to >480 ms (absolute).

New prolongation of QTcF by >60 ms from baseline.

New-onset atrial flutter or fibrillation, with controlled ventricular response rate: ie, rate <120 bpm.

New-onset type I second-degree (Wenckebach) AV block of >30-second duration.

Frequent PVCs, triplets, or short intervals (<30 seconds) of consecutive ventricular complexes.

ECG Findings That May Qualify as SAEs

QTcF prolongation >500 ms.

Absolute value of QTcF > 450 ms AND QTcF change from baseline >60 ms.

New ST-T changes suggestive of myocardial ischemia.

New-onset LBBB (QRS complex >120 ms).

New-onset right bundle branch block (QRS complex >120 ms).

Symptomatic bradycardia.

Asystole:

In awake, symptom-free participants in sinus rhythm, with documented asystolic pauses <math>\geq 3.0</math> seconds or any escape rate <40 bpm, or with an escape rhythm that is below the AV node;

In awake, symptom-free participants with atrial fibrillation and bradycardia with 1 or more asystolic pauses of at least 5 seconds or longer.

Atrial flutter or fibrillation, with rapid ventricular response rate: rapid = rate >120 bpm.

- Sustained supraventricular tachycardia (rate >120 bpm) (“sustained” = short duration with relevant symptoms or lasting >1 minute).
- Ventricular rhythms >30 seconds’ duration, including idioventricular rhythm (HR <40 bpm), accelerated idioventricular rhythm (HR >40 bpm to <100 bpm), and monomorphic/polymorphic ventricular tachycardia (HR >100 bpm [such as torsades de pointes]).
- Type II second-degree (Mobitz II) AV block.
- Complete (third-degree) heart block.

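### The absolute ECG trigger in Protocol 8.3.3 is set on uncorrected QT, while the rules it feeds use QTc or QTcF, so a QTcF above the withdrawal limit can miss both triggers

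*Protocol*

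**What the plan says.** Protocol 8.3.3 lists QT interval and QTcF as separate outputs of the ECG system. It then gives two triggers for extra ECGs after dosing. Trigger (a) is a QTcF rise of at least 60 msec from baseline with QTcF above 450 msec. Trigger (b) reads "or b) an absolute QT value is" at least 500 msec. What follows is mandatory: "If either of these conditions occurs, then 2 additional ECGs will be collected approximately 2 to 4 minutes apart to confirm the original measurement". Criterion (b) appears again, still on QT, among the conditions for continuous monitoring once the abnormality has lasted more than 4 hours.

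The surrounding rules are on corrected QT:

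- **Stopping the repeats (8.3.3):** "a single ECG must be repeated at least hourly until QTc values from 2 successive ECGs fall below the threshold value" that set them off.
- **Cardiologist (8.3.3):** "A cardiologist should be consulted if QTcF intervals do not return to less than the criteria listed above after 8 hours of monitoring".
- **Withdrawal (7.1.2):** "A participant who meets either bulleted criterion based on the average of triplicate ECG readings will be withdrawn from the study intervention". The two criteria are QTcF above 500 ms, and a QTcF change above 60 ms with QTcF above 450 ms.
- **Appendix 8 (10.8):** the QT-related findings of concern are all given as QTcF, including QTcF above 500 ms. Where the appendix speaks of an absolute value, it says "Absolute value of QTcF".
- **Exclusion criterion 14 (5.2), at screening:** if the uncorrected QT exceeds 450 ms, "this interval should be rate-corrected using the Fridericia method only and the resulting QTcF should be used for decision making and reporting".

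No section redefines the QT in trigger (b) as a corrected interval.

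**The concern.** A trigger for confirmatory readings should catch every single reading that could lead to the decision those readings serve. Here withdrawal needs a triplicate average, and the only mandatory post-dose route to a triplicate is 8.3.3. Because QT and QTcF agree only at 60 bpm, a QT threshold is less sensitive than the QTcF withdrawal limit at faster heart rates and more sensitive at slower ones.

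At faster rates, a participant can exceed the withdrawal limit on one ECG without the protocol requiring confirmation. Continuous-monitoring criterion (b) has the same weakness. At slower rates, trigger (b) can fire when QTc is already below the 500 msec used to stop the repeats. That is inconsistent but harmless.

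This is a matter of participant safety and clear site instructions. It does not touch the primary PK comparison.

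**Working it through.** **Inputs.** Triggers (a) and (b) are from Protocol 8.3.3, the withdrawal criteria from 7.1.2, and the 450 ms screening limit from exclusion 14. The conversion is from SAP 3.5.4: QTcF = QT / RR^(1/3), with RR = 60/HR. Hence QT = QTcF × (60/HR)^(1/3). The heart rates are illustrative, as the documents give none. The plan states no figure here to reproduce.

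**Step 1: is withdrawal criterion 2 covered?** It needs a rise above 60 ms and QTcF above 450 ms. Trigger (a) needs a rise of at least 60 ms and QTcF above 450 ms. Every reading that meets the former meets the latter, so none is missed.

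**Step 2: is withdrawal criterion 1 covered?** A reading escapes both triggers when QTcF > 500, the rise is < 60 and QT < 500. The last condition holds when HR > 60 × (QTcF/500)^3.

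| QTcF (ms) | QT is below 500 ms when HR exceeds |
|---|---|
| 501 | 60 × 1.002³ = 60.4 bpm |
| 509 | 60 × 1.018³ = 63.3 bpm |
| 519 | 60 × 1.038³ = 67.1 bpm |

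**Step 3: one example.** Baseline QTcF is 445 ms and on-study QTcF is 502 ms at 70 bpm. The rise is 502 − 445 = 57 ms, so (a) does not fire. QT = 502 × (60/70)^(1/3) = 476.9 ms, so (b) does not fire. Yet 502 ms is above the 500 ms withdrawal limit.

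**Step 4: size of the window.** In whole milliseconds with baseline at or below 450 ms, QTcF must lie between 501 and baseline + 59. Baseline 442 allows one value (501) and baseline 450 allows nine (501-509). The total is 1 + 2 + … + 9 = 45 baseline/QTcF pairs, with rises of 51 to 59 ms. This counts combinations and is not a probability.

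The 450 ms limit applies to the screening ECG only. SAP 3.5.4 takes the last predose ECG in Period 1 as baseline. If that reached 460 ms (an assumption), the window would extend to QTcF 460 + 59 = 519 ms.

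**Step 5: the other direction.** QT of exactly 500 ms corresponds to:

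| HR (bpm) | QTcF (ms) |
|---|---|
| 45 | 454.3 |
| 50 | 470.5 |
| 55 | 485.7 |
| 60 | 500.0 |

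Below 60 bpm, trigger (b) can therefore fire with QTcF already under 500 ms.

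**Step 6: after the change.** With trigger (b) as QTcF of at least 500 msec, all 45 pairs (QTcF 501 or more) fire it. None is missed.

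**The case against.** The strongest reply is that this is an obvious slip that the section corrects itself. The confirmation step speaks of QTc values staying above the threshold, a later sentence refers back to a prolonged machine-read QTc as already defined, and the cardiologist rule speaks of QTcF returning below the listed criteria. All of these assume a QTc threshold. That supports the reading of intent, but it also shows that the section contradicts itself. The section names QT and QTcF separately, so the literal reading remains open to a site.

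The second reply is that a QTcF above 500 ms would be noticed anyway. Appendix 8 lists it as a possible SAE and recommends an alert to the investigator and study team. A qualified person compares each ECG with baseline, and 7.1.2 requires documented review. A site that sees 502 ms cannot apply the withdrawal rule without a triplicate, and "Unscheduled safety measurements may be obtained at any time during the study". This makes a missed triplicate unlikely, but none of these provisions requires one.

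The third reply is scale. The window is a few milliseconds wide, about 12 healthy adults are planned, and Protocol 4.3 describes itraconazole's QTc risk as low. Table 3 appears to schedule one Period 2 ECG besides early termination, after the only Period 2 dose of PF-07817883. Withdrawal at that point could spare at most the remaining itraconazole doses. All of this stands and limits the consequence. Exclusion 14 also governs screening only, so it shows which measure the protocol prefers rather than setting an on-study rule.

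**Conclusion.** The inconsistency is real. Trigger (b) is on uncorrected QT in both places in 8.3.3, while the confirmation, stopping, cardiologist and withdrawal rules are on QTc or QTcF. As written, a single reading above the 500 ms QTcF withdrawal limit can miss both mandatory triggers. The gap is confined to withdrawal criterion 1 with a rise below 60 ms and a heart rate above about 60 to 63 bpm, for a baseline at or below 450 ms. Withdrawal criterion 2 is fully covered.

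This rests on the literal text, on Fridericia correction, and on comparing triggers and limits reading by reading. The chance of a case in this study is small, and no PK result changes. It should still be corrected, because the threshold governs a mandatory safety action and the correction is trivial.

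**What to change.** In Protocol 8.3.3, change QT to QTcF in criterion (b), keeping at least 500 msec, both for the confirmatory ECGs and for continuous monitoring. If an uncorrected-QT alert is also wanted, list it as a separate trigger with a stopping rule on QT. The small difference between the trigger (rise of at least 60 ms) and withdrawal (rise above 60 ms) can stay, because it errs on the safe side.

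The cost is two word changes in one section. In practice it means few, if any, extra ECGs above 60 bpm and fewer confirmatory ECGs below 60 bpm.
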